1 INTRODUCTION

A review published in 2020 reported that an average of 21.7% of contact lens (CL) wearers stop wearing lenses,¹ with discomfort being the main reason for discontinuation.²⁻⁵ One study reported 26.6% of new soft CL wearers stopped wearing lenses over the first year. The most common reasons for discontinuing CL wear were poor distance vision (38%), poor near vision (24%), handling problems (23%) and discomfort (21%).² A study conducted in Canada found 23% permanently discontinued lens wear, with the main reasons being discomfort (24%) and dryness (20%). As we spend an increasing amount of time on digital devices in our daily lives, the number of people potentially dropping out of CL wear may be affected by the use of digital devices. CL wearers suffer from computer vision syndrome more frequently than those who do not wear lenses (65% to 50%), with lens wearers who use computers for >6 hours per day more likely to be symptomatic.⁶ Symptoms related to use of digital devices may be due to multiple reasons, including a decreased blink rate, incomplete blinking, or poor wetting of the lens.⁷⁻⁹

The importance of choosing a suitable contact lens for digital device users was demonstrated in a recent study. Lens wearers who used digital devices for an average of 9.7 hours per day were refit with verofilcon A (PRECISION1[®]) daily disposable CLs.¹⁰ After two weeks of wear, participants were asked to rate the overall comfort, dryness, and clarity of vision using 0 to 100 scale (where 100 was the best rating). Verofilcon A lenses performed well, with mean \pm standard deviation ratings of 91 ± 11 for comfort, 88 ± 11 for dryness, and 92 ± 9 for clarity of vision. Most participants felt verofilcon A provided all-day good comfort (88%) and vision (91%). The majority of participants were also satisfied with the comfort (84%), vision (91%), and overall performance (81%) of the lenses when using digital devices for at least 6 hours.

The purpose of this study is to evaluate the performance of delefilcon A (DAILIES TOTAL1[®]) in habitual contact lens wearers who report substantial digital device use (≥ 8 hours on a typical day).

2 OBJECTIVES

The objective of the study is:

- To refit habitual soft lens wearers, who use digital devices ≥ 8 hours on a typical day, with DAILIES TOTAL1[®] daily disposable CLs, and to assess their subjective ratings (0-100) for overall comfort, overall dryness, and overall clarity of vision during a typical day when using digital devices ≥ 8 hours while wearing DAILIES TOTAL1[®] CLs, reported after two weeks of wear.

The primary outcome variables for this study are:

- Subjective ratings (0-100, where 100=best) of overall comfort, overall dryness and overall clarity of vision with DAILIES TOTAL1® CLs during a typical day when using digital devices ≥ 8 hours (reported after two weeks of wear).

Other outcome variables of interest include:

- Likert type questions exploring the satisfaction with DAILIES TOTAL1® CLs when using digital devices (after two weeks of wear)
- Subjective ratings (0-100, 100=best) of comfort, dryness, and clarity of vision collected using an at home questionnaire on days 1, 7, and 14 ± 1 at three time-points each day: after lens insertion, after 8 hours of digital device use, and at the end of day
- Lens wear time
- Lens fit

3 HYPOTHESIS

DAILIES TOTAL1® will provide a satisfactory performance for substantial digital device users as reflected in subjective ratings of ≥ 75 (0-100 scale, 100=best) for overall comfort, dryness, and clarity of vision during a typical day when using digital devices for ≥ 8 hours, reported after two weeks of wear.

4 MATERIALS AND METHODS

4.1 STUDY DESIGN

4.1.1 OVERALL DESIGN

This is a prospective, non-masked, open-label dispensing study with three study visits on two study days. CL wearers who use digital devices for ≥ 8 hours on a typical day will be enrolled. Eligible participants will be fit and dispensed with DAILIES TOTAL1® study lenses for 14+2 days, to be worn for at least 5 days a week and at least 13 hours per day.

- **Visit 1:** Screening and fitting of study lens (approx. 1.0 hour)
- **Visit 2:** Baseline & Dispense (approx. 0.5 hours; same day as and directly after Visit 1)
- **Visit 3:** Day 14 Follow-up and study exit (approx. 1.0 hour)

4.1.2 RANDOMIZATION

There will be no randomization in this study because all participants will be dispensed with DAILIES TOTAL1®.

4.2 STUDY POPULATION

4.2.1 SAMPLE SIZE

The sample size in this study is based on the previous study with a similar aim and design, involving PRECISION1® contact lenses (PUG, Kuali# 41694).¹¹ That study found meaningful results with a sample size of 32 and therefore the sample size for this study is planned to be the same, with a minimum of 32 participants to complete the study.

4.2.2 NUMBER OF PARTICIPANTS

Participants will be recruited using CORE database and advertising approved by the UW Office of Research Ethics. Up to 35 participants may be dispensed with study products, with a target of 32 completing the study. Informed consent will be obtained for all participants prior to their enrolment in the study.

4.2.3 INCLUSION AND EXCLUSION CRITERIA

A person is eligible for inclusion in the study if they:

1. Are between 18 and 40 years of age (inclusive) and has full legal capacity to volunteer;
2. Have read and signed an information consent letter;
3. Are willing and able to follow instructions and maintain the appointment schedule;
4. Are a digital device user (at least 8 hours on a typical day using any combination of digital devices such as PC, laptop, smartphone or tablet);
5. Are a habitual wearer of daily wear, spherical, soft contact lenses (no bifocal or multifocal contact lenses, no extended wear or monovision) for at least 5 days/week and at least 13+ hours/day on a typical day during the month prior to enrolment;
6. The habitual lens type brand will be restricted such that a maximum of 7 participants will be included in the study for each lens brand/material;
7. Have a vertex corrected spherical equivalent distance refraction within -0.50D to -9.00D in each eye;
8. Have a vertex corrected refractive cylinder ≤ -0.75 cylindrical correction in each eye after vertexing to the corneal plane;
9. Demonstrate an acceptable fit and achieves best corrected visual acuity of at least 0.10 logMAR in each eye with DAILIES TOTAL1® contact lenses;

10. Are willing to wear DAILIES TOTAL1® contact lenses at least 5 days per week and 13+ hours per day throughout the study.

A person will be excluded from the study if they:

1. Are participating in any concurrent clinical or research study involving intervention or invasive ocular tests;
2. Are presbyopic or habitually use a reading addition for close work;
3. Have any known active* ocular disease and/or infection;
4. Meet the diagnosis of dry eye disease as per the following combination:
 - Meets the symptom criteria of CLDEQ-8 score ≥ 12
 - And they show 1 of the following 2 signs:
 - Either NaFl staining (either [cornea >5 dots] or [conjunctiva >9 dots] or [lid margin >2 mm length AND $\geq 25\%$ width]);
 - Or NITBUT (no contact lens) <10 seconds.
5. Have a systemic condition that in the opinion of the investigator may affect a study outcome variable;+
6. Are using any systemic or topical medications that in the opinion of the investigator may affect a study outcome variable;
7. Are a current wearer of DAILIES TOTAL1® daily disposable contact lenses;
8. Have known sensitivity to the diagnostic pharmaceutical sodium fluorescein to be used in the study;
9. Have undergone refractive error surgery;
10. Are a member of CORE directly involved in the study.

* For the purposes of this study, active ocular disease is defined as infection or inflammation which requires therapeutic treatment. Mild (i.e. not considered clinically relevant) lid abnormalities (blepharitis, meibomian gland dysfunction, papillae), corneal and conjunctival staining and mild dry eye are not considered active ocular disease. Neovascularization and corneal scars are the result of previous hypoxia, infection or inflammation and are therefore not active.

+ Any potential exclusion will be reviewed with the Lead Investigator or Principal Investigator prior to final decision making.

Age >40 years is excluded because presbyopia and pre-presbyopia is highly prevalent in this population and will cause eyestrain and impact vision irrespective of the contact lens material, thus impacting subjective ratings.

4.2.4 VULNERABLE POPULATION

This study will not be conducted in vulnerable populations.

4.2.5 REPEATED SCREENINGS

In some circumstances a repeated screening may need to be scheduled (V1-R). Examples include, but are not limited to:

1. Incomplete information available at time of screening to determine eligibility (e.g. current lens brands worn, history from current eye care practitioner etc.)
2. Study procedures unable to be completed in the time scheduled for visit;
3. Study products not available at the time of the screening visit;
4. A transient health condition which may affect the eye(s) (e.g. a common cold, active allergies, fatigue etc;)
5. The short term use of medications (e.g. antibiotics, antihistamines etc.)
6. Reassessment of baseline ocular conditions (e.g. corneal and/or conjunctival staining, scars etc.)

The maximum total number of screenings permitted will be 3; i.e. 2 re-screens are permitted.

4.3 STUDY MATERIALS

4.3.1 LENSES

The study lens is approved by Health Canada. Lenses will be worn bilaterally, and on a daily disposable basis.

Table 1: Lens characteristics

Lens	DAILIES TOTAL1®
Material	delefilcon A
HC licence #	87774
Medical device class	2
Dk/t (barrer/cm) at -3.00D	156
Water content	core 33%, surface ≥ 80%
Sphere power (D)	+0.50 to +6.00 (in 0.25 steps) -0.50 to -6.00 (in 0.25 steps) -6.50 to -12.00 (in 0.50 steps)
Base curve (mm)	8.5
Diameter	14.1
Replacement scheduled	daily disposable

4.3.2 LENS CARE SYSTEM

No lens care system is required because the lenses are daily disposable lenses.

4.3.3 DRUGS

No drugs will be used on the study.

4.3.4 REWETTING DROPS

Participants will not be encouraged to use rewetting drops; however, those who habitually used rewetting drops will be allowed to continue using their normal drops. Rewetting drop use will be recorded at each visit.

4.3.5 ORDERING CONSUMABLES

DAILIES TOTAL1® study lenses will be supplied by Alcon for use in this study.

4.3.6 DISPOSING OF CONSUMABLES

Worn lenses collected during study visits will be discarded as per University of Waterloo regulations.

4.3.7 PRODUCT ACCOUNTABILITY

Accountability logs will be kept to include the number of lenses received, dispensed, unused and returned to sponsor (where relevant). All products dispensed to participants will be recorded in individual participant logs in the study binder.

4.4 SCHEDULED AND UNSCHEDULED VISITS

This study has a total of three study visits on two separate days, including the screening visit (V1) which will typically be conducted immediately prior to the baseline/dispense visit (V2). Participants will attend the clinical site for a total of approximately 2.5 hours. Participants will also be asked to complete at home ratings on Day 1, Day 7, and Day 14±1 to assess their experience with the study CLs.

4.4.1 STUDY VISITS

A summary of the study visits is shown in Table 2.

Table 2: Summary of visits

Visit code	Day	Visits	Duration (hours)
V1	0	Screening	1.0
V2	0	Baseline & Dispense Provide instructions on at-home ratings.	0.5
Given to participant at V2	1, 7, 14±1	Subjective at-home ratings	0.5
V3 & Exit	14 + 2 after V2	Day 14 Follow-up	1.0
Total			3.0

Visits that fall outside of the specified visit windows will be designated as minor protocol deviations and at the end of the study, the data collected during protocol deviations will be assessed for their suitability to be included in the analysis data set.

4.4.2 PRE-SCREENING

A pre-screening questionnaire will be attached to the recruitment email script sent out to participants in the CORE database or to participants expressing an interest in the study to assess whether they would meet the criteria of a habitual soft lens wearer who uses digital devices for ≥8 hours on a typical day and to determine if their level of symptoms while wearing CLs aligns with inclusion/exclusion criteria. If interested, potential participants can return the questionnaires to CORE, or answer the questions over the phone, if preferred. The pre-screening questionnaire is used to minimise screen failures and is not considered study data. Participant eligibility will be determined at a scheduled screening visit, using the inclusion/exclusion criteria listed in Section 4.2.3 after informed consent has been obtained. All study data questionnaires will be completed after informed consent has been obtained.

4.4.3 SCREENING (VISIT 1)

A documented informed consent process will be conducted with all participants prior to their enrolment in the study and prior to any data collection of measurements.

Participants will be assigned a study ID number after they sign the consent documentation, i.e. before their eligibility for the study has been confirmed. The investigator will determine participant eligibility using the inclusion and exclusion criteria. Ineligible participants will be discontinued from the study.

The procedures to be performed are listed below and are explained in more detail in Section 4.5.:

Participants will attend the visit wearing spectacles. Participants will not have worn their contact lenses for at least 12 hours prior to the visit.

1. Informed consent;
2. Participant demographics (age, sex);
3. Participant history:
 - *Medical history/medications;*
 - *Habitual contact lens wear;*
 - *Digital device use.*
4. CLDEQ-8 questionnaire;
5. logMAR distance high illumination, high contrast visual acuity (HIHC VA) with habitual spectacles for OD, OS, and OU;
6. Auto-refraction/auto-keratometry;
7. Non-invasive break-up time;
8. Biomicroscopy examination:
 - *External adnexa anomalies;*
 - *Cornea & anterior eye assessment for scars, infiltrates;*
 - *Bulbar & limbal redness;*
 - *Corneal & conjunctival staining with fluorescein dye;*
 - *Palpebral conjunctival hyperemia and roughness;*
 - *Lid margin staining (horizontal length and sagittal width 0-3 scale; 1 increment).*
9. Subjective spherocylindrical refraction, monocular and binocular logMAR distance HIHC VA;
10. Best sphere refraction, monocular and binocular logMAR distance HIHC VA;

11. DAILIES TOTAL1® fitting:

- i. *The contact lens power will be chosen based on the vertexed best sphere refraction;*
- ii. *The participant will insert the lenses which will be allowed to settle for 5 minutes;*
- iii. *Monocular over-refraction will be performed. If a different lens power is needed, the new power CL will be inserted and steps ii and iii will be repeated;*
- iv. *The final lens powers for OD and OS will be recorded with the monocular and binocular logMAR distance HIHC VA;*
- v. *Acceptability of lens fit (movement, centration; YES/NO) will be confirmed.*

12. Confirm eligibility.

4.4.4 BASELINE AND DISPENSE, DAY 0 (VISIT 2)

1. Participants who successfully meet all the eligibility criteria will proceed directly to Visit 2, while continuing to wear the pair of study lenses that were just fit in Visit 1.
2. logMAR distance HIHC VA with study lenses for OD, OS, OU;
3. Subjective post-insertion ratings (0-100 integer scale, where 100 means best performance; both eyes rated together) to assess the initial impression of DAILIES TOTAL1® regarding:
 - *Comfort;*
 - *Clarity of vision.*
4. Lens fit and surface evaluation:
 - *Lens centration;*
 - *Lens movement in primary gaze;*
 - *Lens tightness on push-up test;*
 - *Surface wettability;*
 - *Surface deposits.*
5. At-home rating scales: Participants will receive at-home rating scales to be completed on Day 1, Day 7, and Day 14±1.
6. Lens wear instructions. The participants will be asked to:
 - *Wear the lenses at least 5 days per week and >13 hours per day throughout the study;*
 - *Complete the subjective at-home ratings to reflect their lens wear experience on Day 1 (the day after V2), Day 7, and Day 14±1 using a 0-100 scale. Ratings will be completed after insertion, after 8 hours of digital device use, and at the end of the day just before lens removal. The final at-home questionnaire will be*

completed the evening before their scheduled Visit 3. Variables to be assessed are:

- *Comfort;*
- *Dryness;*
- *Clarity of vision.*

- *Attend V3 after 8 hours or more of DAILIES TOTAL1® study lens wear.*

7. Dispense lenses.

4.4.5 DAY 14 FOLLOW-UP VISIT AND EXIT, DAY 14+2 (VISIT 3)

Participants will attend the visit after 8 hours of DAILIES TOTAL1® study lens wear.

1. Collect unused study CLs;
2. Changes in medication history/medications;
3. Compliance with # of CL wear days/hour per day with typical # hours of digital device use over the past 2 weeks and for V3 visit day;
4. Collect and review at-home ratings;
5. logMAR distance HIHC VA with study lenses for OD, OS, and OU;
6. Subjective ratings (0-100 scales, where 100 means better performance; integer steps, both eyes rated together), to assess a typical day in the past 2 weeks 5 minutes after insertion, after 8 hours of digital device use, at the end of the day just prior to removal, and overall for:
 - *Comfort;*
 - *Dryness;*
 - *Clarity of vision.*
7. Subjective satisfaction;
8. Lens fit and surface evaluation:
 - *Lens centration;*
 - *Lens movement in primary gaze;*
 - *Lens tightness on push-up test;*
 - *Surface wettability and deposits.*
9. Biomicroscopy examination:
 - *External adnexa anomalies;*
 - *Cornea & anterior eye assessment for scars and infiltrates;*
 - *Bulbar & limbal redness;*
 - *Corneal & conjunctival staining with fluorescein dye;*

- *Palpebral conjunctival hyperemia & roughness.*

10. logMAR distance HIHC VA with habitual spectacles or CLs for OD, OS, and OU.

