4.5 STUDY PROCEDURES

A summary of the study procedures to be conducted at the different scheduled visits is listed in Table 3. Most procedures are described in more detail in the following sub-sections.

Table 3: Summary of procedures to be conducted at scheduled visits

Procedure	Visit 1	Visit 2	Visit 3
	Screening	Baseline & Dispense	Day 14 Follow-up
Informed consent	X		

Participant demographics (age, sex)	X		
Medical history and medications	X		
Changes in medical history/medications			X
Contact lens history	X		
Digital device use history	X		
CLDEQ-8 questionnaire	X		
HIHC VA (logMAR) (habitual spectacles)	X		
Auto-refraction/auto-keratometry: horizontal and vertical K readings	X		
Non-invasive tear film break-up time	X		
Biomicroscopy	X		
Biomicroscopy (without lid margin staining)			X
Subjective refraction	X		
HIHC VA (logMAR) (study CL)	X	X	X
Study lens fitting	X		
Eligibility	X		
Subjective ratings (post-insertion comfort & vision)		X	
Subjective ratings (comfort, dryness, & vision)			X
Satisfaction ratings (Likert scale)			X
Lens assessment (fit, wettability, deposits)		X	X

Provide at-home ratings (comfort, dryness, & vision)		X	
Collect unused study lenses			X
Review of compliance (CL wear, digital device use, completion of at-home ratings)			X
HIHC VA (logMAR) (habitual spectacles or contact lenses)			X

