4.5.9 SUBJECTIVE RATINGS

Subjective ratings:

At visit 2, participants will be provided with subjective rating questionnaires using a 0-100 scale (where 100 = best performance; integer steps, both eyes rated together) to assess their first impression with the study CLs post-insertion regarding comfort and clarity of vision.

At the end of Visit 2, participants will be provided with at-home questionnaires to subjectively rate the experience with study lenses regarding comfort, dryness, and clarity of vision using a 0-100 scale (integer steps; both eyes together), where 100 means better performance. This questionnaire will be completed on Days 1, 7, and 14 ± 1 after Visit 2 (i.e. Day 0), at three different time-points on each of these days: after insertion, after 8 hours of digital device use, and at the end of the day just before lens removal. The final at-home questionnaire will be the evening before their scheduled Visit 3. In addition, times of lens insertion, first notice of discomfort, and lens removal will be collected. There will also be a diary entry for the number of hours of cumulative digital device use that day.

At Visit 3, participants will be provided with subjective rating questionnaires to assess a typical day over the past 2 weeks, to report their experiences i) 5 minutes after insertion, ii) after 8 hours of digital device use, iii) at the end of the day just prior to lens removal, and iv) overall. For each typical timepoint, comfort, dryness, and clarity of vision will be assessed using a 0-100 scale (integer steps; both eyes together), where 100 means best performance.

Satisfaction with study CL:

Satisfaction (5-point Likert scale: strongly disagree, slightly disagree, neither disagree or agree, slightly agree, strongly agree) with DAILIES TOTAL1® CLs overall and while using digital devices on a typical day in the past 2 weeks will be assessed for the following questions:

- *The study lenses provide good vision all day long.*
- *The study lenses provide good comfort all day long.*

- *I am satisfied with the comfort the study lenses provide when I use digital devices for ≥ 8 hours.*
- *I am satisfied with the vision the study lenses provide when I use digital devices for ≥ 8 hours.*
- *I don't experience eye strain when I wear the study lenses and use digital devices for ≥ 8 hours.*
- *I don't experience eye fatigue (tired eyes) when I wear the study lenses and use digital devices for ≥ 8 hours.*

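### The Visit 3 list places compliance questions and review of the home ratings ahead of the primary ratings, an avoidable risk of bias that reordering would reduce at no cost

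*Combined protocol and SAP*

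**What the plan says.** Section 4.4.5 gives Visit 3 as a numbered list. Item 3 is "Compliance with # of CL wear days/hour per day with typical # hours of digital device use over the past 2 weeks and for V3 visit day". Item 4 is "Collect and review at-home ratings". Item 5 is acuity with the study lenses. Item 6 is the set of 0-100 ratings, "to assess a typical day in the past 2 weeks 5 minutes after insertion, after 8 hours of digital device use", then at the end of the day, and overall. Item 7 is satisfaction. Lens evaluation and biomicroscopy follow at items 8 and 9.

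Section 2 defines the primary outcomes as "Subjective ratings (0-100, where 100=best) of overall comfort, overall dryness and overall clarity of vision with DAILIES TOTAL1® CLs during a typical day" with at least 8 hours of device use. These are the overall lines of item 6.

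Section 4.5.9 has the home sheets rate comfort, dryness and clarity on the same 0-100 scale on Days 1, 7 and 14 ± 1, "at three different time-points on each of these days: after insertion, after 8 hours of digital device use, and at the end of the day". It adds: "The final at-home questionnaire will be the evening before their scheduled Visit 3".

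Table 3 in section 4.5 describes the Visit 3 check differently: "Review of compliance (CL wear, digital device use, completion of at-home ratings").

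Section 4.1.1 states: "This is a prospective, non-masked, open-label dispensing study with three study visits on two study days". Section 4.1.2 confirms that everyone receives the same lens.

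**The concern.** The primary outcome should be the participant's own judgement of two weeks of wear. If staff collect and look through the home sheets with the participant first, the participant may try to match or justify scores that staff have just seen. Questions about wear and device hours could, more weakly, prompt answers that please.

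A randomised comparison might share such an effect between arms and cancel part of it. Here there is no second arm. The hypothesis in section 3 is an absolute level of 75, and section 10.1 plans descriptive statistics for the primary outcomes, so any shift passes straight into the reported result. The Likert items at item 7, which section 10.1 analyses by binomial testing, come after the same review. Nothing in the protocol says that the Visit 3 ratings are given first or without sight of the home sheets. Once the visits are over, the exposure cannot be undone.

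**Working it through.** The point concerns the order of procedures, so there is no figure in the plan to reproduce. The sample size of 32 in section 4.2.1 is carried over from an earlier study and not calculated. The check has three parts.

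**1. Is the 4.4.5 list a running order?** No sentence says so. Its content reads like one: acuity and fit with study lenses (items 5 and 8) precede fluorescein staining (item 9), and acuity with habitual correction comes last. Likewise 4.4.3 runs from consent to confirming eligibility, and 4.4.4 ends with dispensing. Table 3 places the compliance review below the ratings rows, but its rows do not follow time. It lists Visit 3 biomicroscopy above lens assessment and study-lens acuity above study lens fitting, and it puts collection of unused lenses, item 1 in 4.4.5, near the end. Table 3 therefore does not settle the order, and staff would naturally follow 4.4.5.

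**2. How far do the home sheets overlap with the Visit 3 ratings?**
- Visit 3: 3 attributes × (3 time-points + overall) = 12 items.
- Home sheet: 3 attributes × 3 time-points = 9 items per day, with no overall item.
- Visit 3 items with a home counterpart: 9 of 12.
- Primary items with a home counterpart: 0 of 3.

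The link to the primary outcome is thus indirect: same attributes, same scale, but not the same question.

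**3. How large would a bias have to be to matter against 75?** The documents give no size for it. As a guide only, take the earlier lens study's means and SDs from section 1 and the target n = 32. The interval is mean ± t(0.975, 31) × SD/√32, with t = 2.04. The half-width is 2.04 × 11/√32 = 2.04 × 1.945 = 3.97 for comfort and dryness, and 2.04 × 9/√32 = 2.04 × 1.591 = 3.25 for vision. The last column subtracts an assumed upward bias of 2, 5 or 10 points.

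| Rating | Mean ± SD | 95% interval | Lower limit minus 75 | Lower limit after removing 2 / 5 / 10 points |
|---|---|---|---|---|
| Comfort | 91 ± 11 | 87.0 to 95.0 | 12.0 | 85.0 / 82.0 / 77.0 |
| Dryness | 88 ± 11 | 84.0 to 92.0 | 9.0 | 82.0 / 79.0 / 74.0 |
| Vision | 92 ± 9 | 88.8 to 95.2 | 13.8 | 86.8 / 83.8 / 78.8 |

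Only dryness with a 10-point bias falls below 75.

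**The case against.** A reader might infer that staff and participant go through all 27 home scores (9 items × 3 days) and that these answers do carry over into the primary ratings. The documents do not support that. Nowhere do they say that scores are read back, shown or discussed. Table 3 speaks only of whether the sheets were completed, and no primary item repeats a home item. That part of the objection stands. It does not remove the risk, because 4.4.5 lists an unqualified review separately from compliance, and even a completion check brings the scored sheets out just before the primary ratings.

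Other points also stand:
- Anchoring could raise or lower a rating, and questions about device hours could help recall of a typical day.
- Item 3 collects wear and device hours, not ratings, and participants already know the wear requirement from inclusion criterion 10 and the dispensing instructions.
- Participants will remember the sheet they filled in the evening before, whatever the order at the visit.
- The ratings already precede the lens and slit-lamp examinations.
- Section 10.1 plans no analysis of agreement between home and Visit 3 ratings, so no planned analysis of that kind is at stake.

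A reader might also conclude that the overall items must be asked before the time-point items. That is a preference in questionnaire design. Rating the time-points first may equally support a considered overall judgement, and nothing in the documents shows that it biases the answer.

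**Conclusion.** The point holds as an avoidable risk. The listed order permits the home scores and compliance to be gone over before the primary and satisfaction ratings, and no text prevents it, in a study with no masking and no control arm. Whether any carry-over would occur, how large it would be and in which direction cannot be derived from the documents.

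Severity is minor. On the earlier study's figures, an upward bias would have to exceed roughly 9 to 14 points, depending on the attribute, to change the reading against 75. That range assumes that this lens is rated like the earlier one, that 32 participants complete, and that the hypothesis is read as the lower 95% limit of the mean lying above 75, which the protocol does not specify. It concerns only the threshold; a smaller bias would still distort the reported means.

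**What to change.** In section 4.4.5:
- Move items 6 and 7 ahead of items 3 to 5.
- State that participants complete both themselves, without sight of the home sheets.
- Then collect and review the home sheets and ask about compliance.
- Use the same description of the review in 4.4.5 and Table 3, saying whether it covers completion only or also the scores.

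The cost is renumbering one list and adding a sentence, with no extra time, staff or procedure. Moving acuity has one side-effect: section 4.4.4 lists acuity before the Visit 2 ratings, so the two visits would then differ in that respect. If the sponsor prefers to keep them parallel for the Visit 2 to Visit 3 comparison in section 10.1, acuity can stay first; placing the ratings ahead of items 3 and 4 is what matters. The change removes fresh exposure to the scores in front of staff. It does not remove memory of the previous evening's sheet, and the report should say so.
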